The PINNACLE Registry® is the largest outpatient cardiovascular clinical data registry in the world, with millions of patients drawn from thousands of sites around the US representing over 10,000 outpatient providers. The registry has a comprehensive goal of improved patient care. In addition to using the PINNACLE Registry®, non-PINNACLE sites within large health systems will be recruited and randomized into the intervention and usual care arms respectively.

[figure not shown]
The Specific Aims of this study will be:

- To evaluate ability of ACC Solution Sets and Patient Resources to improve initiation and titration
 of GDMT for eligible patients with HFrEF Left Ventricle Ejection Fraction (LVEF) ≤ 40%.
- To evaluate change in QOL between patients in the Intervention arm and the Usual Care arm.
- Examine relative change in GDMT among higher risk versus lower risk patients in the Intervention arm and Usual Care arm.

In this randomized registry trial, sites will be invited to participate in a 6-month study aimed at various processes of care in HFrEF. Sites would be informed that they might be asked to participate in an intensive intervention to improve GDMT prescription or in a study of QOL in HFrEF. Once a list of sites interested in participating is created, sites would be randomized into two arms: an intervention group and a usual care group.

AMERICAN

(**Figure 1**): This graphic shows both usual care and intervention arm tracts.

Study Population:

- Patients from practices participating in the PINNACLE Registry® (these include those that are
 part of integrated health systems, stand-alone, and other practice environments); as well as
 patients from other practices (these include those that are part of integrated health systems,
 stand-alone, and other practice environments) with pre-existing data interfaces with study
 partner HealthReveal.
- Patient cohorts will have the following **inclusion** criteria:
 - Age ≥18 years
 - Clinical diagnosis of HF with EF ≤40% documented within 1 year of enrollment
 - Receiving ≥1 oral medication for HF at study enrollment (including diuretics, ACEI/ARB/ARNI, beta-blockers, MRA, SGLT2i or thiazide diuretics.
- Patient cohorts will have the following **exclusion** criteria:
 - Current or anticipated participation in a clinical trial
 - Currently receiving comfort care or enrolled in hospice
 - Life expectancy <1 year
 - o History of or plan for heart transplantation or left ventricular assist device

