Adult patients ages 18 years and older with heart failure with Left Ventricle Ejection Fraction (LVEF) \leq 40% will be identified via an initial data extraction from interested sites. Participating sites will receive a roster of eligible patients, in order to best plan their enrollment. There will be no discrimination or bias with respect to patient inclusion on the basis of sex, race, or religion.

5. Subject Recruitment and Compensation

Upon identification of eligible patients, members of the clinical team will approach the patient with the offer to participate in a clinical study.

At **Intervention sites**, patients will be presented with the goals of the study, and given time to review the Informed Consent (prepared in their own language). Following, if the patient agrees, consent will be signed and patient included in the trial.

At **Usual Care sites**, patients will be presented with a proposal for periodic HFQoL assessment. If the patient agrees, consent will be signed and patient included in the trial.

No compensation will be offered to patients or families for participation in the registry or study.

6. Consent Process

Study consent will be provided electronically ("e-consent"), using Medable software. Consent materials will be provided with sufficient time for the patient to consider their participation in the study. For patients in the Intervention Arm of the study, consent materials will describe the study procedures, expected risks and expected benefits. For patients in the Usual Care arm, consent materials will only focus on the KCCQ-23. All consent materials will be in the patients' native language.

If the patient agrees to participation in the study, their informed consent will be recorded through e-consent processes with signature stored at Medable.

At any time, patients may withdraw consent. In such a circumstance, patients will be analyzed per intent to treat.

7. Subject's Capacity to Give Legally Effective Consent

Only those patients capable of giving informed consent will be enrolled in the study.

8. Study Interventions

In the Intervention arm, for each study visit, the site will receive a pre-visit assessment of GDMT accompanied by recommended adjustment(s) using information extracted weekly from the sites' EHR.

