Using this approach, each patient may contribute to the numerator or be in the denominator 1, 2, 3 or 4 times, depending on meeting criteria and if eligible in that domain. An advantage of this composite approach is that it allows for a holistic view of all classes of drugs considered and allows for assessment not only of up-titration but also down-titration as well.

Example of a patient without contraindications:

Therapy	Initial dose	≥50% target?	Final dose	≥50% target?
Sacubitril/valsartan	24/26 mg twice daily	No	96/104 mg twice daily	Yes
Carvedilol	6.25 mg twice daily	No	12.5 mg twice daily	Yes
Spironolactone	25 mg daily	Yes	25 mg daily	Yes
	Ratio = 0 + 0 + 1/1 +1 + 1= .33		Ratio = 1 + 1 + 1/1 + 1 + 1 = 1.0	
	Relative change = 66.7%			

Example of a patient with contraindication to spironolactone (previous hyperkalemia):

Therapy	Initial dose	≥50% target?	Final dose	≥50% target?
Sacubitril/valsartan	24/26 mg twice daily	No	49/51 mg twice daily	Yes
Carvedilol	6.25 mg twice daily	No	6.25 mg twice daily	No
	Ratio = 0 + 0 /1 +1= .000		Ratio = 1 + 0/1 + 1 = .50	
	Relative change = 50.0%			

Example of a patient with no contraindication to spironolactone but not receiving it:

Therapy	Initial dose	≥50% target?	Final dose	≥50% target?
Sacubitril/valsartan	24/26 mg twice daily	No	24/26 mg twice daily	No
Carvedilol	6.25 mg twice daily	No	6.25 mg twice daily	No
Spironolactone	0	No	25 mg daily	Yes
	Ratio = 0 + 0+ 0 /1 +1 + 1 = .000		Ratio = 0 + 0 +1/1 + 1 + 1 = .33	
	Relative change = 33.0%			

In the CHAMP-HF Registry, the score at baseline was 34.7%, while at 6 months it increased nominally to 36.3% ([name], *Confidential Personal Communication, January 2019*).

Secondary endpoints; compared to usual care:

- 1) Relative change in actual achieved doses of individual classes of pivotal therapies (RASi/beta blocker/ MRA/SGLT2i).
- 2) Relative change in achievement of target doses (yes/no) of pivotal therapies (RASi/beta blocker/MRA/SGLT2i).

Exploratory, compared to usual care:

- 3) Difference in patient-reported outcome/KCCQ-23 scores from baseline to 6 months.
- 4) Rate of \geq 25%, \geq 50%, \geq 75% and 100% improvement in scores.
- 5) Among those not taking an evidence-based beta blocker, % changed to evidence-based beta blocker during course of the study.
- 6) Change in % eligible taking RASi during course of the study.
- 7) Change in % eligible taking beta blocker during course of the study.

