- 8) Change in % eligible taking MRA during course of the study.
- 9) Change in % eligible taking SGLT2i during course of the study.
- 10) Relative improvement in GDMT composite score among subgroups of interest. This may include pre-specified analyses among patients the following characteristics:
 - a. Elderly patients (age ≥ 75 years)
 - b. New onset HF
 - c. Recently hospitalized patients
 - d. Those with LVEF <25%
 - e. Those with estimated glomerular filtration rate <30 mL/min/1.73m²
 - f. Baseline systolic blood pressure <100 mm/Hg
 - g. Absence of RASi at baseline
 - h. Absence of beta blocker at baseline
 - Patients with high baseline total medication burden (5 or more meds for all conditions)
 - j. Academic versus Private practice

Power calculations: The primary endpoint will compare central tendency in score changes between the two groups (6-month score - baseline score; this gives a range of score changes from -3 to +3). We will assume a 5% rate of score decreases, with rates for -3, -2 and -1 assumed equal between the two groups. To compare such changes a two-sided Wilcoxon ranksum test at a 0.05 significance level with 90% power will be employed. Assuming 5% of usual

care patients have an increase in score versus 10% of the intervention arm change by 1 point, a sample size of 2560 (1280 per arm) would be needed. Assuming a reasonable 20% loss to follow-up and/or missingness in this registry analysis, this makes a total of 3072 (1536 per arm). This not only provides power for the primary endpoint, but also for the secondary and exploratory endpoints, including change in QOL metrics.

12. Data and Safety Monitoring

This is an observational study comparing the effectiveness of two standards of care based on secondary use of data collected in the conduct of care and patient reported outcomes. The purpose of this study is not to gather data with regards to the safety profile and/or effectiveness of specific drugs. This study does not proscribe which treatment patients will receive. There is no Data Safety Monitoring Board for this study.

Adverse events (should they occur) will be captured at the clinical site level. Patients reporting adverse events will address these with their providing physician.

13. Data Storage and Confidentiality

Please refer to the Data Management section for details regarding how data captured in this study is stored and how the confidentiality of such data is maintained.

References

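### The primary test treats patients as independent although whole sites are randomised, so its 5% error rate does not hold

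*Protocol*

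**What the plan says.** Section 3 (Design and Procedures) sets the unit of randomisation: "sites would be randomized into two arms: an intervention group and a usual care group". It says the same of practices outside the registry: "non-PINNACLE sites within large health systems will be recruited and randomized into the intervention and usual care arms respectively". Section 8 (Study Interventions) delivers the intervention at the same level: "for each study visit, the site will receive a pre-visit assessment of GDMT". Section 5 divides recruitment by intervention sites and usual care sites, so every enrolled patient of a site is in one arm.

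Section 11 builds the endpoint patient by patient: "each patient may contribute to the numerator or be in the denominator 1, 2, 3 or 4 times". The power paragraph in that section then names the test of the resulting score changes: "To compare such changes a two-sided Wilcoxon ranksum test at a 0.05 significance level with 90% power will be employed". No other primary analysis is named.

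The protocol does not mention clustering, an ICC, a design effect, the number of sites, a site effect or a robust variance.

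**The concern.** The rank-sum test takes its null variance from the assumption that all patients' score changes are independent. When sites are allocated, the arm comparison is a comparison of groups of sites. Any tendency of patients at one site to change together adds variance that the test does not count. The standard error is then too small and the p-value too low, as would be any interval built on the same variance.

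Such a tendency is to be expected on the protocol's own reasoning. Section 2 attributes under-treatment partly to clinicians: inertia, limited confidence about targets, and reluctance to change therapy in patients who seem stable. Patients of one practice share these influences. The endpoint's denominator also depends on whether a reason for a lower dose was documented, so local record-keeping enters the score. Sites within one large health system may be correlated with each other as well.

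At stake is the primary conclusion: ordinary differences between sites could be reported as an effect of the intervention.

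**Working it through.** **1. The plan's own sample size.** Section 11 gives these inputs: 5% of patients with a decrease in both arms; an increase in 5% under usual care and in 10% (by 1 point) under the intervention; two-sided alpha 0.05; 90% power. I place the usual-care increases at +1 as well. This leaves 90% and 85% unchanged.

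- P(intervention > control) + ½P(tie) = 0.095 + 0.0425 + 0.00125 + 0.3825 + 0.0025 = 0.52375.
- The pooled proportions are 0.05/3 for each of three decreases, 0.875 and 0.075. The tie factor is 1 − Σp³ = 0.3296.
- Noether's formula with this tie factor: N = (1.960 + 1.282)² × 0.3296 / (12 × 0.25 × 0.02375²) ≈ 2047, or 1024 per arm.

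The protocol states 1280 per arm. Spreading the usual-care increases over +1 to +3 gives 1185, which does not match either. Since 1024/0.80 = 1280, the stated figure may already contain the 20% loss. Even if the factor 1280/1024 = 1.25 were an unstated design effect, enlarging the sample would not correct the variance used by the test.

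**2. Error rate of the named test.** With m analysed patients per site, the variance is inflated by DE = 1 + (m − 1) × ICC, and the true two-sided error is 2 × [1 − Φ(1.96/√DE)].

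The protocol gives neither m nor the ICC, so both are assumed. For m, the registry cited in Section 2 offers an illustration: 3518 patients / 150 practices = 23.5. Example at ICC 0.02: DE = 1 + 22.45 × 0.02 = 1.449; 1.96/√1.449 = 1.628; error = 10.3%.

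| Patients per site | ICC 0 | 0.01 | 0.02 | 0.05 | 0.10 |
|---|---|---|---|---|---|
| 10 | 5% | 6.0% | 7.1% | 10.4% | 15.5% |
| 23.5 | 5% | 7.7% | 10.3% | 17.9% | 27.7% |
| 50 | 5% | 10.8% | 16.4% | 29.1% | 42.0% |
| 100 | 5% | 16.5% | 25.6% | 42.2% | 55.3% |

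**3. Check by simulation.** Both arms were given the usual-care distribution, with site-to-site variation from a Dirichlet-multinomial model (5000 replicates per setting). The tie-corrected rank-sum test was compared with a t-test on site mean ranks.

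| Sites × patients | Test | ICC 0 | 0.01 | 0.02 | 0.05 | 0.10 |
|---|---|---|---|---|---|---|
| 110 × 23 | rank-sum | 4.8% | 7.4% | 10.3% | 17.2% | 28.8% |
| 110 × 23 | site-level | 5.0% | 5.0% | 4.9% | 4.6% | 5.0% |
| 50 × 51 | rank-sum | 4.8% | 10.6% | 15.4% | 29.8% | 41.1% |
| 50 × 51 | site-level | 4.8% | 4.8% | 4.3% | 4.6% | 4.8% |

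A second simulation, with a site effect on a latent scale, gave similar results: at 55 sites of 23 per arm, 7%, 11%, 16% and 26% at ICC 0.008, 0.02, 0.04 and 0.09.

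**4. Power of a valid test.** With 2560 patients analysed at 23.5 per site, power = Φ(3.242 × √(2560/(N₀ × DE)) − 1.96), where N₀ is the sample giving 90% power under independence.

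| | ICC 0.01 | 0.02 | 0.05 | 0.10 |
|---|---|---|---|---|
| Power, N₀ = 2047 (recomputed) | 91% | 85% | 70% | 52% |
| Power, N₀ = 2560 (as stated) | 83% | 77% | 60% | 44% |
| N for 90% power, 2048 × DE | 2508 | 2968 | 4348 | 6647 |
| N for 90% power, 2560 × DE | 3135 | 3710 | 5435 | 8309 |

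The values of N are before any allowance for loss to follow-up.

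**The case against.** The sentence stands in the power paragraph and can be read as a sample-size assumption. Handling of site is often settled in a statistical analysis plan, and one may exist. But the protocol says that this test will be used and names no other. A plan with a clustered analysis would contradict it, and the sentence would still need correcting.

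The size is not known. The ICCs are assumed, the 23.5 per site comes from another study, and the larger sites have no source in the protocol. This stands, and the figures are a range for that reason. The direction does not depend on them.

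The endpoint is a change from baseline, which subtracts stable differences between sites in prescribing level. This also stands in part: it argues for weighting the lower ICCs and smaller sites, where the error is about 6% to 11%. It does not remove site differences in titration over the six months, which is the behaviour the intervention targets.

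Lastly, a valid test has less power for the same number of patients, so the correction is not free. That is right and is counted in the cost below.

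**Conclusion.** The concern holds. The protocol randomises sites and fixes a primary test that is valid only for independent patients, so the stated 0.05 is not the error rate for any positive within-site correlation. At ICC 0.01 to 0.05 the error is about 8% to 18% with 23.5 patients per site and 11% to 29% with 50. It falls to 5% only at an ICC of zero, which the protocol's own account of clinician behaviour makes implausible. The exact excess cannot be derived from the protocol. For a given ICC it grows with the number of patients per site, so enrolling more patients at the same sites makes it worse. This must be corrected before the primary comparison is made.

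**What to change.** Replace the patient-level rank-sum test in Section 11 with an analysis that respects site randomisation. Two forms are suitable:

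- **Model-based.** A mixed model, or GEE with small-sample correction, for the 6-month composite score. Fixed effects are arm, baseline composite score and registry versus non-registry practice; the mixed model adds a random site effect and bases its degrees of freedom on the number of sites. This gives an effect estimate and interval. The two covariates serve precision; the error rate is restored by the handling of site.
- **Rank-based.** A clustered rank-sum test or a site-level permutation test on the change scores. This stays closest to the comparison now described.

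In either case, report the estimated ICC and state the number of sites. Where several sites belong to one health system, say how that further level is handled.

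The analysis change is one of wording and needs no new data, since the baseline score is already collected. The cost is greater, and correctly stated, uncertainty. The 90% power should be recalculated with an assumed ICC and site size: at 23.5 per site and ICC 0.02, 2560 analysed patients give about 85% (77% if 2560 is itself the independent-patient requirement). Restoring 90% may need more sites or patients.

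### The 20% loss allowance is applied as a multiplication by 1.20, so 3072 should read 3200 if 2560 evaluable patients are needed; 2560 itself cannot be confirmed from the inputs given

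*Protocol*

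**What the plan says.** All the inputs are in Protocol section 11, Power calculations. The endpoint is the change in score from baseline to 6 months, and "this gives a range of score changes from -3 to +3". The test and error rates are given as: "To compare such changes a two-sided Wilcoxon ranksum test at a 0.05 significance level with 90% power will be employed". On worsening, the text says: "We will assume a 5% rate of score decreases, with rates for -3, -2 and -1 assumed equal between the two groups". On improvement, it contrasts 5% of usual-care patients with 10% of intervention patients. The one-point size is attached to the intervention figure, and no separate size is given for the usual-care increases.

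From this it concludes that "a sample size of 2560 (1280 per arm) would be needed". The loss allowance comes next: "Assuming a reasonable 20% loss to follow-up and/or missingness in this registry analysis, this makes a total of 3072 (1536 per arm"). The same paragraph then relies on this total for the secondary and exploratory endpoints, including quality of life.

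**The concern.** The two figures do different jobs. The first is the number of patients who must contribute data. The second is the number to enrol so that this many remain after 20% are lost. A loss is a fraction of those enrolled, so the second figure is the first divided by 0.80. The printed total is instead the first figure raised by 20%, which leaves the trial short of its own stated requirement if the assumed loss occurs.

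The first figure should also follow from the stated test, error rates and response rates. If it does not, a reader cannot tell what power the trial has, or how much room there is if loss exceeds 20%.

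**Working it through.** **Loss step.** The plan's own figure first: 2560 × 1.20 = 3072, and 1280 × 1.20 = 1536 per arm. This reproduces the printed total exactly.

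- Needed to retain 2560 after 20% loss: 2560 / 0.80 = 3200, or 1280 / 0.80 = 1600 per arm.
- Remaining from 3072 after 20% loss: 3072 × 0.80 = 2457.6, about 2458 (1229 per arm).
- Shortfall in evaluable patients: 2560 − 2458 = 102. Shortfall in enrolment: 3200 − 3072 = 128.
- Loss that 3072 can absorb: 1 − 2560/3072 = 16.7%.

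**Base step.** For a rank-sum test on ordered categories with 1:1 allocation, the tie-corrected total is

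N = (z₀.₉₇₅ + z₀.₉₀)² × T / [3(θ − 0.5)²].

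Here θ is the probability that an intervention patient scores higher than a usual-care patient, counting ties as one half. T is 1 minus the sum of the cubed category probabilities averaged over the arms. The squared sum of the z values is 10.507.

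Simplest reading, with every increase equal to one point:

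- Usual care: 5% decrease, 90% no change, 5% at +1. Intervention: 5%, 85%, 10% at +1.
- The 5% of decreases is split evenly over −3, −2 and −1 in both arms.
- θ = 0.05 × 0.025 + 0.85 × 0.50 + 0.10 × 0.975 = 0.52375.
- T = 1 − (3 × 0.0167³ + 0.875³ + 0.075³) = 0.3296.
- N = 10.507 × 0.3296 / (3 × 0.02375²) ≈ 2047, or 1024 per arm.

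Putting all decreases at −1 gives 2046. Simulated power was 0.898 at 1020 per arm, 0.945 at 1229 and 0.952 at 1280.

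The size of the usual-care increases is not stated, so it was varied with the intervention increases held at +1. Power is Φ(√[3N(θ − 0.5)²/T] − 1.960).

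| Usual-care 5% increases | θ | N for 90% power | Power at 2560 | Power at 2458 |
|---|---|---|---|---|
| All +1 | 0.52375 | 2047 | 95.2% | 94.4% |
| Spread evenly over +1 to +3 | 0.52208 | 2369 | 92.1% | 91.0% |
| All +2 or +3 | 0.52125 | 2559 | 90.0% | 88.8% |

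The last row matches the printed 2560. On the simplest reading, other calculations do not recover it at the stated settings: 6209 without the tie correction, 1668 one-sided, 1529 at 80% power, 1164 comparing two proportions, and 2080 by a t-test with all decreases at −1. At 95% power N is 2531, which is close, but the protocol states 90%.

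**The case against.** The strongest defence concerns the base figure. The protocol does not give enough to fix N, so 2560 has not been shown to be a miscalculation. Placing all usual-care increases at two points or more is an odd planning assumption, but it contradicts nothing in the text and returns the printed number at the stated power. That stands. The supportable criticism is that the assumed distribution is missing and the simplest reading gives about 2047. The detailed category probabilities may also sit in a statistical analysis plan that is not shown. That does not excuse the loss step, which the protocol itself states and gets wrong.

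A reader might infer that 2560 already contains the 20% allowance, because 2048 / 0.80 = 2560 exactly, and that the allowance was then made twice. The text presents 2560 as the number required and introduces loss only afterwards, so this rests on a numerical coincidence.

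A reader might also take the 5% decrease rate to apply at each of −3, −2 and −1, giving 15% in all, N of about 4140 and only 72% power at 2560. The wording describes a 5% rate of decreases overall and then says that the rates at each level match between the arms. It does not support 15%.

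Finally, it can be said that the consequence is small. That also stands: the enrolment gap is 128 of 3200, or 4%.

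**Conclusion.** The loss step is wrong as written and depends on no interpretation: 2560 evaluable patients after 20% loss require 3200 enrolled, not 3072. The base figure is unconfirmed rather than proven wrong. It is about 25% above the simplest reading (2560/2047 = 1.25) and is recovered at 90% power if the usual-care increases are all two points or more, an assumption that is not stated.

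It would be tempting to conclude that the trial is underpowered. The arithmetic does not show that. With 2458 evaluable patients, power is between about 89% and 94% across the placements checked. These figures assume independent patients. Sites are randomised, so clustering matters, but it is a separate question and is not counted here. This should be fixed, but it does not threaten the trial by itself.

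**What to change.** In section 11, tabulate the assumed probability of each score change from −3 to +3 in each arm, including the size of the usual-care increases, and give the base number that follows from it. Divide that number once by 0.80. Then choose one of two statements:

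- If 2560 is kept as the evaluable number, correct the total to 3200 (1600 per arm).
- If 3072 is kept as the enrolled number, say that it leaves 2458 evaluable after 20% loss and give the power under the stated distribution: about 94% on the simplest reading, or about 89% on the one that yields 2559, both before any allowance for clustering.

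The cost is a recalculation and a protocol wording change. The second option leaves enrolment as planned; the first adds 128 patients.

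### The claim that the sample size also powers the secondary and exploratory endpoints has no calculation behind it, and under the protocol's own planning effect it fails for the subgroups and for class-by-class target-dose achievement

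*Protocol*

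**What the plan says.** The power paragraph in Protocol Section 11 plans one comparison, the change in the composite score, by a "two-sided Wilcoxon ranksum test at a 0.05 significance level with 90% power will be employed". For decreases it says: "We will assume a 5% rate of score decreases, with rates for -3, -2 and -1 assumed equal between the two groups". For increases, 5% of usual "care patients have an increase in score versus 10% of the intervention arm change by 1 point". From this it concludes that "a sample size of 2560 (1280 per arm) would be needed", and then enlarges the number: "Assuming a reasonable 20% loss to follow-up and/or missingness in this registry analysis, this makes a total of 3072 (1536 per arm").

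The next sentence extends the claim: "This not only provides power for the primary endpoint, but also for the secondary and exploratory endpoints, including change in QOL metrics". No effect size, SD, class-specific rate or subgroup size is given for any endpoint it covers.

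Those endpoints include:
- actual achieved dose by class (secondary 1);
- "Relative change in achievement of target doses (yes/no) of pivotal therapies" (secondary 2), for RASi, beta blocker, MRA and SGLT2i;
- the change in KCCQ-23 (exploratory 3);
- the composite score in ten listed subgroups (exploratory 10), among them patients without RASi at baseline, patients without a beta blocker at baseline, and "Those with estimated glomerular filtration rate <30 mL/min/1.73m"².

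**The concern.** The sentence states a property of the design as fact. It is not a detail left for an analysis plan. A sample sized for one effect in all patients has less power for the same effect in a subset. Likewise, a score that adds up movement over several drug classes can be well powered while the individual classes are not.

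What is at stake is the reading of null results. With this sentence in the protocol, a non-significant class-level or subgroup result could be presented as adequately powered evidence of no effect. The third specific aim compares higher-risk with lower-risk patients, and the Background motivates the trial partly by under-treatment of high-risk patients. The subgroup results will therefore be looked at closely.

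**Working it through.** **Inputs.** From the power paragraph: two-sided 0.05; 90% power; 5% decreases in each arm (taken as 1.67% at each of −3, −2, −1); +1 in 5% versus 10%; no change in 90% versus 85%; 1280 evaluable per arm. From Section 2 (Background and Significance): 27% of eligible registry patients without RASi and 33% without a beta blocker. Clustering by site is ignored throughout because the protocol gives no intra-site correlation. Any positive correlation would lower every figure below.

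**Formula** (rank-sum test with tie correction). With θ = P(intervention > control) + ½P(tie) and T = 1 − Σ p̄³ over the score categories:
- n per arm = (z₀.₉₇₅ + z_power)² × (T/6) / (θ − 0.5)²
- power = Φ( (θ − 0.5)√n / √(T/6) − 1.96 )

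**1. The protocol's own figure.** θ = 0.52375 and T = 0.3296.
- n for 90% = 3.2415² × 0.05494 / 0.02375² = 1023.4, so 1024 per arm, not 1280.
- At 1280 per arm: 0.02375 × 35.78 / 0.2344 = 3.625, and Φ(3.625 − 1.96) = 95.2%.

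The stated N is thus somewhat generous for the primary endpoint under this formula. The figure 1280 equals 1024/0.80, so losses may already be in it, but the protocol does not say so. The checks below use the full 1280, which favours the protocol's claim.

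**2. Subgroups, same effect.** In a fraction f of the sample, power = Φ(3.625√f − 1.96).

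| Subgroup | f | n per arm | Power | Power if 1280 gives exactly 90% |
|---|---|---|---|---|
| No RASi (registry share) | 0.27 | 346 | 47% | 39% |
| No beta blocker (registry share) | 0.33 | 422 | 55% | 46% |
| Half the sample | 0.50 | 640 | 73% | 63% |

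The last column replaces 3.625 by 3.2415.

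**3. Class-level achievement (secondary 2).** Assume that it uses the primary's threshold of 50% of target dose. A one-point gain is then one class crossing the threshold, and the 5-point excess in gains is divided among classes. Let a class carry share s of all movement: −1 in 5s% of both arms, +1 in 5s% versus 10s%.

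For s = 0.25 the increases are 1.25% versus 2.5%, θ − 0.5 = 0.00617 and T = 0.0908. Power = Φ(0.00617 × 35.78 / 0.1230 − 1.96) = Φ(−0.165) = 43%. In the same way:

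| Share of movement in the class | Power at 1280 per arm |
|---|---|
| 1/4 (even over four) | 43% |
| 1/3 (even over three) | 55% |
| 1/2 (even over two) | 72% |
| 60% | about 80% |
| 80% | about 90% |

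The shares sum to one, so a class at 60% leaves 40% for the rest. At an even four-way split, 90% power in a class needs about 4177 per arm. The protocol does not state how movement divides among classes, so the even splits are illustrations. That the classes cannot all be well powered does not depend on them. In a random search over uneven splits, using a simple comparison of increases only (64% per class at an even four-way split), the weakest of four classes stayed below about 72%.

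**4. KCCQ.** The protocol gives no SD. Assume an SD of 15 to 25 and a design effect (DE) of 1 to 2.1. The difference detectable at 90% is 3.2415 × SD × √(2·DE/1280):
- SD 15, DE 1: 1.9 points
- SD 25, DE 2.1: 4.6 points

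**5. Actual achieved dose (secondary 1).** Nothing in the protocol allows a power calculation.

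**The case against.** **QOL.** A reader might infer that the sentence is false for every endpoint it covers, QOL included. The documents do not support that. QOL is the one outcome the sentence names, and the assumed ranges above give no sign of a shortfall: even at SD 25 and design effect 2.1, power for an illustrative 5-point difference is about 94%. The claim there lacks support, but nothing contradicts it.

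**Secondary endpoints.** Secondary 1 also counts dose changes that do not cross 50% of target, so it is not a fraction of the primary's movement. Secondary 2 speaks of target doses, while the primary uses half of target. If full target is meant, the event and its rates differ and the dilution argument does not carry over. Both objections stand, so the class-level point is conditional. A class carrying most of the movement would also be adequately powered.

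**Subgroups.** They are labelled exploratory, and the list is introduced as one that may be used. A larger effect in under-treated patients is plausible: 5% versus 15% would give about 94% power at 27% of the sample. That is fair, but the protocol plans no such effect, and a power claim must rest on a stated one. A reader might also assume that several subgroups are very small; at 10% of the sample power would be about 21%. The protocol gives no prevalence for them, so that figure is only illustrative.

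**Consequence.** No test, sample size or decision rule depends on the sentence. This is true and limits the weight of the point, but it does not make the statement correct.

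**Conclusion.** The concern holds in limited form. The sentence has no supporting calculation. Under the protocol's own 5% versus 10% effect it is wrong for the composite score in subgroups. It is also wrong as a claim about every drug class in secondary 2, provided that endpoint uses the 50% threshold.

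The subgroup result rests on an unchanged effect and on registry shares carrying over to this trial; a larger true subgroup effect would raise power. The figures for individual classes rest on assumed splits.

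The point does not show that the trial is too small for its primary endpoint. Before clustering, the stated N exceeds what the stated inputs require.

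**What to change.** Delete the sentence, or limit the power claim to the primary endpoint. State that class-level and subgroup results will be given as estimates with confidence intervals and carry no power claim. Keep a claim for QOL only with a stated SD for KCCQ change, the detectable difference at the planned evaluable N, and the allowance made for site randomization.

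This is a wording change. No endpoint, visit or sample size is affected. The cost is a less favourable statement about what the trial can show.
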